5.3.5. Time to response (TTR)

TTR is defined in Section 4.1.5.

TTR (months) will be described by population/cohort using mean, standard deviation, median, maximum, and minimum.

5.3.6. Progression-free survival (PFS)

PFS is defined in Section 4.1.6.

According to population/cohort, the Kaplan-Meier method will be used to analyze the median PFS, the corresponding 95% CI will be calculated using the Brookmeyer-Crowley method, and the PFS plot will be drawn. The proportion of subjects with PFS greater than or equal to 6/9/12 months will also be analyzed. The Kaplan-Meier method will be used to analyze the 6-, 9-, and 12-month PFS rates, and the corresponding two-sided 95% CIs will be calculated (using the log(-log) transformation by normal approximation with back transformation).

The K-M curve of PFS of apatinib 250 mg + SHR1210 200 mg (Stage I) vs. apatinib 375 mg + SHR1210 200 mg will be plotted.

5.3.7. 12-month overall survival rate (12-OS%)

12-OS% is defined in Section 4.1.7.

The Kaplan-Meier method will be used to analyze the 12-OS% of each population/cohort, and the corresponding two-sided 95% CI will be calculated (using the log(-log) transformation by normal approximation with back transformation).

5.3.8. Overall survival (OS)

OS is defined in Section 4.1.8.

The Kaplan-Meier method will be used to analyze the median overall survival of each population/cohort, its 95% CI will be calculated using the Brookmeyer-Crowley method, and the survival curve will be plotted. The proportion of subjects with OS greater than or equal to 12/18/24 months will also be analyzed. The Kaplan-Meier method will be used to analyze 12-, 18-, and 24-month overall survival rates and the corresponding two-sided 95% CIs will be calculated (using the log(-log) transformation by normal approximation with back transformation).

The K-M curve of OS of apatinib 250 mg + SHR1210 200 mg (Stage I) vs. apatinib 375 mg + SHR1210 200 mg will be plotted.

5.3.9. Change in tumor size (CTS)

CTS is defined in Section 4.1.9. The waterfall plot of the maximum change in tumor size will be plotted.

5.3.10. Exploratory analyses

Based on the FAS, the 4 groups including driver gene negative population, driver gene negative population (non-squamous cell carcinoma), driver gene positive population, and cohort 4 will be analyzed (in terms of ORR, PFS, and OS) using SHR-1210-related tumor biomarkers, such as PD-L1 expression levels on tumor cells (TC) in tumor tissues ($\text{PD-L1} \geq 1\%$ or $< 1\%$), TAM (TAM expression \geq median or $<$ median), tumor mutation burden in plasma ($\text{bTMB} \geq 1.54$ muts or < 1.54 muts), tumor mutation burden in tissues ($\text{tTMB} \geq$ median or $<$ median), and proportion of positive PD-L1 expression on circulating tumor cells (CTC) ($\text{PD-L1} \geq 1\%$ or $< 1\%$), including calculation of ORR and its 95% CI, median PFS and OS and their 95% CIs.

Driver gene negative population (non-squamous cell carcinoma) refers to 1) Apatinib 250 mg + SHR1210 200 mg (Stage I): subjects who are negative or not tested for EGFR and also negative or not tested for ALK fusion gene; 2) Cohort 1: non-squamous, non-small cell lung cancer with wild-type EGFR and ALK.

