2.2 Endpoints

Primary endpoints:

Stage I:

Incidence and severity of adverse events (AEs) and serious adverse events (SAEs)

Stage II:

Tumor objective response rate (ORR)

Secondary endpoints:

Stage I:

Plasma concentrations of SHR-1210 and apatinib

Pharmacokinetic parameters of SHR-1210 and apatinib, including $t_{1/2}$; C_{max} ; AUC, etc.

Tumor objective response rate (ORR)

Stage II:

Incidence and severity of adverse events (AEs) and serious adverse events (SAEs)

Stages I and II:

Clinical benefit rate (CBR): Proportion of subjects with CR, PR, or SD ≥ 6 months during the study

Duration of response (DoR)

Time to response

Progression free survival (PFS) based on RECIST 1.1

12-month survival

Overall survival (OS)

Exploratory analysis of the relationship between biomarkers and efficacy

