3.3 Collection of Biomarker Samples

For all enrolled subjects, their blood samples will be collected at baseline. For subjects showing CR/PR during the study, their blood samples will be collected during the first evaluation of CR/PR and the first evaluation of PD, with 10 mL of blood samples collected each time (14 mL of blood will be collected at baseline and divided into two tubes, with 10 mL in one tube and 4 mL in the other tube). These blood samples will be sent to the central laboratory for blood-based detection of tumor mutation burden (TMB), while the detection of circulating tumor cells (CTC) and the detection of PD-L1 based on circulating tumor cells (CTC) will also be performed in the baseline period. See the central laboratory manual for blood sampling, disposal, and transportation.

For subjects participating in the Stage II of the study, their tumor tissue samples will be collected at baseline. Among these tumor tissue samples, 3-5 slices of 3-4 µm thick paraffin tissue sections will be sent to the central laboratory for the detection of levels of PD-L1 and tumor-associated macrophages (TAM) in tumor tissues; 5-8 slices of 5-8 µm thick tumor biopsy samples or paraffin tissue sections collected before the first dose will also be sent to the central laboratory

for the detection of TMB level in tumor tissues. The biopsy samples can be directly sent to the central laboratory through cold chain transportation. Paraffin blocks can be directly sent to the central laboratory without mounting onto slides. See the central laboratory manual for tissue sampling and transportation.

In order to avoid the impact of previous treatment on tumor mutation burden, the tumor tissue samples should be collected from biopsy or surgical resection carried out at a time point closest to the first dose for the detection of TMB levels.

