Cohort 4. Non-squamous and non-small cell lung cancer with wild-type EGFR and ALK and with bTMB ≥ 1.54 muts/Mb or tTMB > 10 muts/Mb confirmed by central laboratory, and patients in the stage of a palliative treatment who have received no systemic treatment.

5. ECOG PS: 0-1;
6. Life expectancy ≥ 12 weeks;

7. Major organ functions must meet the following rules (not including the use of blood components or cell growth factors during screening):
 - Absolute neutrophil count $\geq 1.5 \times 10^9/L$;
 - Platelets $\geq 100 \times 10^9/L$;
 - Hemoglobin ≥ 9 g/dL;
 - Serum albumin ≥ 3 g/dL;
 - Thyroid stimulating hormone (TSH) \leq ULN (In the case of abnormalities, FT3 and FT4 levels should also be measured. If FT3 and FT4 levels are normal, the patient can be enrolled);
 - Total bilirubin \leq ULN;
 - ALT and AST $\leq 1.5 \times$ ULN;
 - AKP $\leq 2.5 \times$ ULN;
 - Serum creatinine $\leq 1.5 \times$ ULN or creatinine clearance ≥ 60 mL/min (using the standard Cockcroft-Gault formula, as shown in Appendix 3);
8. Female patients of a childbearing age who are not surgically sterilized should adopt a medically approved contraceptive measure (such as an intra-uterine contraceptive device, contraceptive pills or condoms) during the study treatment period and within 3 months after the end of the study treatment; female patients of a childbearing age who are not surgically sterilized must have a negative serum or urine HCG test result within 72 h prior to study enrollment, and must not be in the lactation period; male patients should be surgically sterilized or agree to use an appropriate contraceptive measure during the study period and within 3 months after the last dose of the study drug;
9. Patients must participate voluntarily, sign the informed consent form, have good compliance, and cooperate with follow-up visits.

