[Biomarker sampling/sample collection and detection] Archived paraffin-embedded tumor samples or fresh biopsy specimens will be collected to make ≥ 10 slices, of which 3-5 slices of 3-4 μm tumor sections (mounted slides) will be collected for the histochemistry detection of biomarkers such as PD-L1, and 5-8 slices of 5-8 μm paraffin sections (paraffin rolls can be directly collected without being mounted on the slides) or fresh biopsy specimens will be collected for the detection of biomarkers such as tumor mutation burden (TMB). Refer to the laboratory manual for details on tumor tissue sampling/sample collection and disposal methods.

For cohort 4, the test results of tumor mutation burden (TMB) in the peripheral blood and/or tumor tissues will be verified before the subjects take the first dose of the study drug, so the TMB test for cohort 4 must be completed before the first dose. However, the delay in the screening period caused by TMB testing is allowed, but other tests (including imaging examinations) must be completed within 21 days prior to the first dose.

Unless otherwise stated, the following screening procedures must be completed within 7 days prior to the first dose:

[Hematology] White blood cell count (WBC), absolute neutrophil count (ANC), lymphocyte count (LYM), red blood cell count (RBC), hemoglobin (Hb), and platelet count (PLT);

[Urinalysis] Urine protein (Note: if urine protein $\geq 2+$, 24-h urine protein quantification test shall be performed), urinary red blood cells, urinary white blood cells, and urine glucose;

[Routine stool test] Occult blood; re-examination is required for fecal occult blood+; if fecal occult blood is confirmed, then a gastroscopy shall be performed. Performed within 7 days before enrollment, on Day 15 of Cycle 1 and Day 1 of subsequent cycles, and upon completion of the study;

[Blood biochemistry] bilirubin total, bilirubin conjugated, ALT, AST, AKP, γ -GT, protein total, albumin, urea or urea nitrogen, creatinine, uric acid, fasting blood glucose, TG, cholesterol, potassium, sodium, chlorine, calcium, phosphorus, blood lipase (only checked in the screening period and in the case of subsequent abdominal pain, abdominal distension and other symptoms of suspected pancreatitis), blood amylase (only checked in the screening period and subsequent abdominal pain, abdominal distension and other symptoms of suspected pancreatitis);

[Coagulation function] Including INR, APTT, PT, TT, and FIB;

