
Cohort 1. Non-squamous, non-small cell lung cancer with wild-type EGFR and ALK;

Cohort 2. Non-small cell lung cancer with EGFR mutation or ALK fusion gene rearrangement. The subjects harboring sensitive EGFR mutations and ALK fusion gene rearrangement must have failed the treatment of at least one EGFR inhibitor or ALK inhibitor;

Cohort 3. Non-central squamous cell lung cancer;

Cohort 4. Non-squamous and non-small cell lung cancer with wild-type EGFR and ALK and with bTMB ≥ 1.54 muts/Mb or tTMB > 10 muts/Mb confirmed by central laboratory.

The enrolled subjects are treated until the occurrence of any event that meets the criteria for discontinuation, so as to further evaluate the efficacy and safety of SHR-1210 in combination with apatinib in patients with advanced NSCLC.

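### In Cohort 4 the planned split at bTMB 1.54 is confounded with tTMB by the entry rule, so it has no TMB-low comparator

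*SAP*

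**What the plan says.** Cohort 4 enrols patients who are high on either TMB measure. SAP 2.1 defines it as wild-type, non-squamous disease "with bTMB ≥ 1.54 muts/Mb or tTMB > 10 muts/Mb confirmed by central laboratory". Protocol 5.1 has the same rule and adds that the patients have had no systemic treatment. Protocol 7.1 has TMB checked before the first dose, and either source may be used: "the test results of tumor mutation burden (TMB) in the peripheral blood and/or tumor tissues will be verified".

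Protocol 2.2 lists among the secondary endpoints: "Exploratory analysis of the relationship between biomarkers and efficacy". SAP 5.3.10 carries this out in four groups: the driver gene negative population, its non-squamous subset, the driver gene positive population and Cohort 4. For the last two it reads: "driver gene positive population, and cohort 4 will be analyzed (in terms of ORR, PFS, and OS) using SHR-1210-related tumor biomarkers". One marker is "tumor mutation burden in plasma ($\text{bTMB} \geq 1.54$ muts or < 1.54 muts"; tTMB is divided at its median. The output for each level is ORR with a 95% CI and median PFS and OS with 95% CIs. No test is planned, and SAP section 3 disclaims any hypothesis or inference.

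SAP 5.3.10 gives no cross-classification of bTMB by tTMB, no adjustment, no exception for Cohort 4 and no caveat. It does not say in which population the tTMB median is taken.

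**The concern.** The number used to divide Cohort 4 by bTMB is the number used to admit patients to it. A patient below that cut can have entered only through the tissue route. The table would present bTMB-high against bTMB-low, but the second group is made up entirely of patients who are high on the other TMB measure, and nobody in the cohort is low on both.

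High TMB defines this cohort, and the biomarker-efficacy relationship is a listed endpoint. If bTMB-low patients did as well as or better than bTMB-high patients, the table would invite the conclusion that bTMB carries no information or works in reverse. That pattern can come from the entry rule alone, provided tTMB affects outcome.

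**Working it through.** **Inputs from the documents.** The entry rule (SAP 2.1, Protocol 5.1); the bTMB cut of 1.54 and the tTMB median cut (SAP 5.3.10); 20 patients, from an ORR of 50% and a 90% CI width of 0.4 (SAP 2.3); Clopper-Pearson intervals (SAP 5.3.2).

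**Inputs assumed.** Marker prevalences, the association between the markers, and effects on response. The documents give none of these.

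**1. The plan's own figure.** The Clopper-Pearson 90% interval at a proportion of 0.5 has width 0.406 for n = 19 and 0.396 for n = 20. The smallest n with width at most 0.4 is 20, so the stated size is reproduced.

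**2. The deduction.**

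| | tTMB > 10 | tTMB ≤ 10 |
|---|---|---|
| bTMB ≥ 1.54 | admitted | admitted |
| bTMB < 1.54 | admitted | not eligible |

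Within Cohort 4, P(tTMB > 10 given bTMB < 1.54) = 1. For bTMB-high patients the rule selects nothing further, so P(tTMB > 10 given bTMB ≥ 1.54) keeps its unselected value.

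**3. Only tTMB matters.** Let d be the ORR gain from high tTMB, a = P(tTMB high given bTMB high), and c = P(tTMB high given bTMB low) in unselected patients. The ORR difference, bTMB-high minus bTMB-low, is then:

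- unselected: d × (a − c)
- Cohort 4: d × (a − 1), which is never positive

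*Strong effect:* ORR 50% against 15% (d = 35 points), 30% high on each marker, and 9%, 15% or 20% high on both. Then a = 0.09/0.30, 0.15/0.30 or 0.20/0.30, and c = 0.21/0.70, 0.15/0.70 or 0.10/0.70.

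| High on both | a | c | Unselected | Cohort 4 |
|---|---|---|---|---|
| 9% (independent) | 0.300 | 0.300 | 0 | 35 × (0.300 − 1) = −24.5 |
| 15% | 0.500 | 0.214 | +10.0 | 35 × (0.500 − 1) = −17.5 |
| 20% | 0.667 | 0.143 | +18.3 | 35 × (0.667 − 1) = −11.7 |

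*Moderate effect:* base ORR 20%, odds ratio 2.5. The odds are 0.25 × 2.5 = 0.625, so the ORR is 0.625/1.625 = 38.5% and d = 18.5 points. Nine scenarios were simulated with 1,000,000 patients each: latent correlation 0, 0.3 or 0.6, crossed with bTMB/tTMB prevalences of 30/30%, 50/30% or 50/50%. Here a ran from 0.30 to 0.70. The Cohort 4 difference was −12.9 to −5.5 points, against 0 to +7.5 unselected. The formula agrees: 18.5 × (0.30 − 1) = −12.9 and 18.5 × (0.704 − 1) = −5.5.

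**4. The other cases** (same nine scenarios, odds ratio 2.5 for each marker that matters).

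| What affects response | Unselected | Cohort 4 |
|---|---|---|
| Both markers | +20 to +29 points | +7 to +16 points |
| Only bTMB | +18.5 | +18.5 |
| Neither | 0 | 0 |

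One further case: any high marker gives 45%, otherwise 15%, with independent markers at 30%. Unselected bTMB-low ORR is 15 + 30 × 0.21/0.70 = 24%, a difference of 21 points. Cohort 4 shows 45% against 45%.

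**5. The tTMB median split.** In the simulation the below-median group was 76% to 100% bTMB-high and the other half 30% to 80%. The below-median group is bTMB-high by necessity only if the median is at or below 10. With correlation 0.6 and 50% prevalence for each marker, the halves were nearly balanced (76% and 78%).

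**6. Precision.** The bTMB-low share of Cohort 4 was 11% to 41%, or about 2 to 8 of 20 patients. An observed ORR of 50% has an exact 95% CI of 27% to 73% with 20 patients, 12% to 88% with 6, and 7% to 93% with 4.

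**The case against.** The case against acting is substantial. The section is exploratory, has no test, and belongs to an SAP that disclaims inference. TMB is not among the named variables for the subgroup forest plots (SAP 5.1.4, 5.3.11). With perhaps 2 to 8 patients in the low group, the intervals are too wide to persuade anyone of a reversal. The Cohort 4 figures would truly describe the patients enrolled; the mistake would lie in generalising them, which the SAP does not do. The same splits are already planned in three populations not enrolled on TMB. Cohort 4 is also the only untreated cohort, so deleting its TMB output loses something.

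Most of this stands, and it limits the weight of the point. It does not remove it. Wide intervals express sampling error; the confounding would be the same at any sample size, and nothing in the SAP warns the reader of it.

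A further objection is that reporting by qualifying route brings the same contrast back, because the tTMB-only group is the bTMB-low group. That is partly true. But three groups show what two conceal: patients high on both can be set beside the tTMB-only group with tTMB above 10 in each.

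A reader might infer more than the documents support:

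- *That the comparison is simply a selection artefact.* Distortion requires that tTMB affects outcome, and the documents do not establish this.
- *That both TMB splits must be deleted.* The exact deduction covers bTMB only.
- *That the PD-L1, tumor-associated macrophage (TAM) and circulating tumor cell (CTC) splits fail as well.* The entry rule does not use those markers.

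**Conclusion.** The point holds for the bTMB split in Cohort 4. The structural part needs no assumed numbers: every eligible bTMB-low patient has tTMB above 10, so the split has no TMB-low comparator. It takes the cut in SAP 5.3.10, printed in muts, to mean muts/Mb, and it assumes no eligibility deviations.

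The consequence is conditional. If only tTMB matters, the Cohort 4 ORR difference runs about 6 to 25 points in the wrong direction; the upper end needs the strong assumed effect of 50% against 15% and independent markers. If both matter, the difference shrinks. If only bTMB or neither matters, it is undistorted. The tTMB median split is exposed to the same problem, but not by necessity.

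The Cohort 4 ORR, and the primary ORR analysis generally, do not use these splits and are unaffected. This is an inexpensive correction to an exploratory analysis of a listed endpoint.

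**What to change.** In SAP 5.3.10:

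- For Cohort 4, replace the bTMB high/low contrast with a bTMB by tTMB cross-table. Describe ORR, PFS and OS by qualifying route (bTMB only, tTMB only, both). Label this as not a comparison of marker-high with marker-low patients, and put the same note on the tTMB median split.
- Give the cross-table a category for a missing result, because entry may rest on blood or tissue alone.
- Base any TMB-efficacy conclusion on the driver gene negative population, its non-squamous subset and the driver gene positive population. Report tTMB above 10 versus at most 10 there, alongside the median, so that the enrolment cut is examined. The present plan names only the median.
- Keep the PD-L1, TAM and CTC analyses as they are.

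The cost is SAP wording and a few changed exploratory tables. No new samples are needed: Protocol 3.3 already collects blood from all subjects and tissue from Stage II subjects. The downsides are small cells in Cohort 4, and that the other three populations were previously treated, so their TMB results do not carry over directly to untreated patients.

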A single-arm/double-arm, multicenter, open-label clinical study.

According to the results of tolerability observation in Stage I and upon the discussion between the sponsor and the principal investigators, 250 mg of apatinib, q.d. oral + 200 mg of SHR-1210, IV, q2W are selected for the Stage II study.

Patients of advanced NSCLC who have failed first-line chemotherapy or patients of non-squamous and non-small cell lung cancer with a high tumor mutation burden (TMB) confirmed by the central laboratory will be enrolled in the Stage II study. According to the molecular and pathological classifications, the subjects are divided into:

Cohort 1. Non-squamous, non-small cell lung cancer with wild-type EGFR and ALK;

Cohort 2. Non-small cell lung cancer with EGFR mutation or ALK fusion gene rearrangement. The subjects harboring sensitive EGFR mutations and ALK fusion gene rearrangement must have failed the treatment of at least one EGFR inhibitor or ALK inhibitor;

Cohort 3. Non-central squamous cell lung cancer;

Cohort 4. Non-squamous and non-small cell lung cancer with wild-type EGFR and ALK and with bTMB ≥ 1.54 muts/Mb or tTMB > 10 muts/Mb confirmed by central laboratory.

The enrolled subjects are treated until the occurrence of any event that meets the criteria for discontinuation, so as to further evaluate the efficacy and safety of SHR-1210 in combination with apatinib in patients with advanced NSCLC.

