13 STATISTICAL ANALYSIS

13.1 Determination of Sample Size

The sample size in Stage I is primarily based on clinical considerations, and the number of subjects actually enrolled in each dose group is determined by the number of subjects who show clinically significant toxicity during the observation period for tolerability. During the expansion stage of PK study, 10-12 subjects are required for each group. The sample size in Stage I is 40-60 subjects.

In Stage II, for cohort 1, assuming that the ORR of the combination therapy is 30% with a bilateral alpha of 0.05, enrollment of 62 subjects will have a 80% power to ensure that the ORR of the combination therapy has a lower 95% CI limit of > 15%. If the dropout rate is 20%, 78 subjects should be enrolled.

For cohorts 2 and 3, assume that the ORR point estimate of each cohort is 30% and the width of the 90% confidence interval is 0.3, 38 subjects are required for each group when a 20% dropout rate is considered.

For cohort 4, assume that the ORR point estimate is 50% and the width of the 90% confidence interval is 0.4, 20 subjects are required to be enrolled.

In Stage II, the four cohorts require to enroll a total of 174 subjects.

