13.2 Statistical Hypotheses

The primary endpoint in Stage II is ORR.

Null hypothesis: $ORR = 15\%$

Alternative hypothesis: $ORR \neq 15\%$

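### SAP 5.3.10 examines tissue TMB and TAM only as median-split groups, so the biomarker–efficacy relationship gets no effect estimate and the measured values go unused

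*SAP*

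**What the plan says.** Protocol 2.2 includes, in the secondary endpoints for Stages I and II, "Exploratory analysis of the relationship between biomarkers and efficacy". Protocol 13.4.6 says biomarkers will be analysed descriptively, and SAP section 3 rules out formal hypotheses and inference.

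SAP 5.3.10 is where this endpoint is analysed. For the driver gene negative population, its non-squamous part, the driver gene positive population and Cohort 4, it forms two groups per marker:

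- tTMB and TAM are cut at the median.
- PD-L1 on tumor cells, PD-L1 on circulating tumor cells and blood TMB are cut at fixed values. The blood TMB cut, 1.54, is the one used for entry to Cohort 4.

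The output named is "including calculation of ORR and its 95% CI, median PFS and OS and their 95% CIs". SAP 5.3.12 and 5.6 add nothing, and the subgroup list in SAP 5.3.11 does not include tTMB or TAM.

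For tTMB, the trial's own definition of high burden is in Protocol 3.1 (Cohort 4): "or tTMB > 10 muts/Mb confirmed by central laboratory". SAP 5.3.10 does not use that value for tTMB.

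**The concern.** A relationship between a marker and an outcome needs an effect measure. Two separate response rates with their intervals, or two separate medians, leave the reader to subtract one from the other by eye. Nothing in SAP 5.3.10 says how strongly response or survival changes with tTMB or TAM, or how uncertain that change is.

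The split also treats every value on one side of the median as the same. In the driver-positive population each half would hold about 19 Stage II subjects (38/2). With 6 responders of 19, for example, the exact 95% interval runs from 13% to 57%. A graded relationship could easily go unseen.

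Two further points limit the use of the tTMB table. A sample median cannot be carried to another dataset or compared with the protocol's threshold of 10. The SAP also does not say whether the median is pooled or taken within each population. If it is taken within each, a Cohort 1 subject could be labelled high in the non-squamous driver-negative table and low in the driver-negative table that contains it.

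**Working it through.** **Inputs from the documents.** Response rate and alpha come from the Cohort 1 design in Protocol 13.1: "assuming that the ORR of the combination therapy is 30% with a bilateral alpha of 0.05". Planned sizes come from the same section: "If the dropout rate is 20%, 78 subjects should be enrolled" for Cohort 1, and "38 subjects are required for each group when a 20% dropout rate is considered" for Cohorts 2 and 3. Protocol 3.3 and inclusion criterion 3 in 5.1 plan baseline tumor tissue for Stage II subjects, so Stage I subjects are left out for these two tissue markers. Using the population definitions in SAP section 5, the planned sizes before missing samples are:

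- driver-negative: Cohorts 1 and 3, 78 + 38 = 116
- driver-negative non-squamous: Cohort 1, 78
- driver-positive: Cohort 2, 38

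Cohort 4 is selected on TMB and is left aside.

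**The plan's own figure.** The SAP and protocol state no power for the biomarker analysis. The one power statement in the documents is for Cohort 1: "enrollment of 62 subjects will have a 80% power". It reproduces. With n = 62 the Clopper-Pearson lower limit first exceeds 15% at 16 responders (15.5%). P(X ≥ 16) is 80.3% at ORR 30% and 1.9% at ORR 15%. Then 62/(1 − 0.20) = 77.5, so 78.

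**Assumptions not in the documents.** The marker is normal on its analysis scale, log-odds of response are linear in it, and the effect is an odds ratio of 1.5 or 2.0 per SD. A two-sided 5% likelihood-ratio test is used purely as a measuring device.

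**Approximate formula.** Splitting a normal marker so that a share p lies above the cut keeps a fraction φ(z)²/[p(1 − p)] of the information, where z is the cut in SD units. At the median this is 0.3989²/0.25 = 0.637 (that is, 2/π). The test's expected z-value shrinks by √0.637 = 0.798.

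- n = 38: continuous power 45% means 1.96 − 0.126 = 1.834. Then 1.834 × 0.798 = 1.464, and Φ(1.464 − 1.96) = 31%.
- n = 78: 75% means 1.96 + 0.674 = 2.634. Then 2.634 × 0.798 = 2.102, and Φ(0.142) = 56%.
- n = 116: 90% means 1.96 + 1.282 = 3.242. Then 3.242 × 0.798 = 2.587, and Φ(0.627) = 73%.

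**Simulation, ORR 30%, odds ratio 2.0 per SD.**

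| n | Continuous | Median split | Difference (points) |
|---|---|---|---|
| 38 | 45% | 30% | 15 |
| 78 | 75% | 56% | 19 |
| 116 | 90% | 74% | 16 |

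Repeat runs agree to within about two points.

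**How far this depends on the assumptions.**

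- Weaker effect, odds ratio 1.5: n = 38, 22% against 16%, a gap of about 5 to 6 points depending on the test; n = 78, about 36% against 25%.
- PFS or OS, Cox score test, about 76% of subjects with events (assumed): n = 78, hazard ratio 0.67 per SD, 85% against 65%; n = 38, hazard ratio 0.74, 33% against 24%.
- Right-skewed marker with an effect linear on the raw scale, odds ratio 2.0 per SD: n = 78, 74% against 38%.
- True step at the median, ORR 15% below and 45% above: n = 78, continuous 66%, split 86%. The sign reverses.

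**A cut at 10 instead of the median.** The share above 10 muts/Mb is not given. The formula keeps 58% of the information if 30% are above the cut, 49% if 20% are, and 34% if 10% are, against 64% at the median. At n = 78 and odds ratio 2.0, with 20% above, simulated power is 49% against 56% for the median split.

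**The case against.** The strongest reply is that nothing planned is lost. The endpoint is labelled exploratory, Protocol 13.4.6 promises descriptive statistics, and SAP section 3 rules out inference. A reader might infer from the power figures that the plan gives up some 10 to 20 points of power. The documents do not support that: they set no test, alpha or effect size for this analysis, and the figures compare two tests that neither document plans. This part of the objection stands. It does not remove the missing effect estimate, because an odds or hazard ratio with its interval is itself descriptive.

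The size also depends on a log-linear effect that no document states, and a true threshold at the median would favour the split. That stands too, and is a reason to keep the group tables beside the model.

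A reader might also infer that the median shifts from population to population, that TAM is certainly continuous, or that no other summary is allowed. The SAP does not say how the median is taken. It gives no scale for TAM, though a median split implies at least an ordered one. Its wording introduces both the markers and the outputs as examples.

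Finally, it is tempting to replace the median by the protocol's cut of 10. Under the same model an off-median cut discards more information, and with 10% above it the driver-positive high group would be about 4 of 38. The case for 10 is comparability, so it should be an added table.

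**Conclusion.** The point holds as a low-cost improvement to an exploratory analysis. SAP 5.3.10 names no estimate of the relationship that Protocol 2.2 lists, and no named output uses the measured tTMB and TAM values. If the relationship is graded, log-linear and moderate, the median split discards about a third of the information (1 − 0.64). That is equivalent to roughly 15 to 19 power points in a hypothetical test at planned tissue populations of 38 to 116. The gap is about 5 to 6 points at n = 38 with an odds ratio of 1.5, and it reverses for a step at the median. Missing tissue samples would reduce all three population sizes. No primary conclusion, sample size or planned error rate is affected.

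**What to change.** In SAP 5.3.10, for the driver-negative, driver-negative non-squamous and driver-positive populations:

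1. Add logistic regression for ORR and Cox regression for PFS and OS. Enter tTMB on a log scale that handles zeros, for example log2(tTMB + 1), and TAM per SD if it is recorded on a continuous scale. Report the odds or hazard ratio with a 95% CI.
2. Label these as exploratory estimates without multiplicity control. Two markers, three outcomes and three populations give 2 × 3 × 3 = 18 estimates, and at n = 38 with ORR 30% only about 11 responders support the logistic model.
3. Keep the median tables as description, and state whether the median is pooled or taken within each population.
4. Add, without substituting, a tTMB table at > 10 against ≤ 10 muts/Mb so that results can be set against the protocol's own threshold.

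The cost is a few lines of SAP text and some model runs on data already planned for collection. The price is an assumed log-linear form, which the retained group tables help the reader to check.
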